| WPB | Personal Data Protection Act (in Dutch: Wet Bescherming Persoonsgegevens) |
| WMO | Medical Research Involving Human Subjects Act (in Dutch: Wet Medisch-wetenschappelijk Onderzoek met Mensen) |

SUMMARY

Rationale: Approximately half of rehabilitating patients do not fully adhere to their prescribed home exercise program, resulting in dissatisfactory treatment outcomes. One factor involved in several aspects of non-adherence and important for physiotherapy is self-efficacy, or one's belief in his or her ability to engage in specific behaviours that will yield a desired outcome. Empowering patients with location-specific reminders, digital instructions and digital feedback options in home exercise programmes may improve their self-efficacy and benefit therapy adherence.

Objective: To study a potential improvement in self-efficacy when using the so-called sticky reminders as compared to usual care without this intervention and to assess user experiences with the sticky reminder intervention.

Study design: This pilot is a controlled mixed methods feasibility study.

Study population: Rehabilitating adult patients suffering from Neuralgic Amyotrophy and rehabilitating adult wearers of a leg prosthesis following home exercise programmes for physiotherapy.

Intervention (if applicable): Introduction and use of an intervention encompassing reminders and an app that transform written and verbal feedback and instructions into digital feedback and instructions.

Main study parameters/endpoints: Self-efficacy quantified with Exercise Self-Efficacy Scale questionnaire before and after 4 weeks of using the application; User experience (patient and physiotherapist); System usability quantified using the System Usability Scale questionnaire after using the app; Frequency of application use; Feasibility of using this app.

Nature and extent of the burden and risks associated with participation, benefit and group relatedness: Participants in the study will be asked to download the application and make use of the reminders and app for four weeks. During these four weeks, the verbal feedback during usual physiotherapy sessions will be filled in briefly, daily and digitally. Before and after the intervention period, they will complete short questionnaires (approximately 10-15 minutes) and frequency of use will be logged. User experiences will be assessed with semi-structured interviews. Participation in the study does not result in any physical or physiological discomfort.

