2. OBJECTIVES

Primary Objective:

To study whether NFC-equipped sticky reminders increase physiotherapy self-efficacy in home exercise programmes as compared to usual care in rehabilitating patients suffering from Neuralgic Amyotrophy or a lower extremity amputation over a period of 4 weeks.

Secondary Objective(s):

To assess the usability of the app and user experiences with NFC-equipped sticky reminders for home exercise programmes in physiotherapy as perceived by rehabilitating patients suffering from Neuralgic Amyotrophy or a lower extremity amputation and how this could be improved.

Other Objective(s)

To determine whether the intervention is used, and thus whether observed effects in intervention group could be caused by the intervention.

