8. METHODS

8.1 Study parameters/endpoints

8.1.1 Main study parameter/endpoint

We will assess the self-efficacy during exercising. Self-efficacy reflects an individual's belief in his or her ability to engage in specific behaviours that will yield a desired outcome. Self-efficacy beliefs are important because the belief that one can exercise, even given constraints and impediments such as feeling tired or being busy, is associated with a greater likelihood of doing it (Neupert *et al.*, 2009).

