8.1.2 Secondary study parameters/endpoints (if applicable)

User's experiences:

- Usability (layout, interface, ease of use, relevance of content, etc.)
- Perceived barriers and facilitators for using the sticky reminders and the app within one's daily routine. It is not being used as part of clinical care
- Perceived positive and negative effects of the sticky reminders and the app

Healthcare Professionals' Perspective

- Usefulness of information from the sticky reminder app.
- Perceived barriers and facilitators for using the information from the sticky reminders plus app within one's daily workload. How does this affect their workload?

Feasibility

- Users' experiences
- Effect on self-efficacy
- Potential as an empowering tool for physiotherapy exercises

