8.1.3 Other study parameters (if applicable)

[figure not shown]
- Frequency of App use. To prove that observed effects could be a result of the intervention, we will determine app usage. We will calculate how often (times per day) the App is used during the research period
- Demography. In the questionnaires, we will ask for age, gender, marital status, medical history (regarding physiotherapy), estimated years affected by symptoms or disorder, employment and highest educational level.

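### The Summary lists five unordered main endpoints and ties the ESES to app use, whereas section 8.1 has self-efficacy alone as main and no section names the between-group ESES contrast that would answer the primary objective

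*Protocol*

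**What the plan says.** The Summary, under its heading for main parameters, reads "Main study parameters/endpoints: Self-efficacy quantified with Exercise Self-Efficacy Scale questionnaire before and after 4 weeks of using the application; User experience (patient and physiotherapist" and, once that bracket closes, continues "System usability quantified using the System Usability Scale questionnaire after using the app; Frequency of application use; Feasibility of using this app". That makes five items with no ranking.

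The body is organised differently:

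- Section 2 has one primary objective: "To study whether NFC-equipped sticky reminders increase physiotherapy self-efficacy in home exercise programmes as compared to usual care". Usability and user experiences form the secondary objective. Whether the intervention is used comes under other objectives.
- Section 8.1.1, the main endpoint, says "We will assess the self-efficacy during exercising" and then explains what self-efficacy means. It names no questionnaire, time point or comparison.
- Section 8.1.2, secondary, covers users' experiences (including usability), the professionals' perspective and feasibility. One of the feasibility items is "Effect on self-efficacy".
- Section 8.1.3, other, has "Frequency of App use. To prove that observed effects could be a result of the intervention, we will determine app usage".
- Section 10.1 plans before-after tests of the ESES, described as both within and between the two groups. It calls the correlations of self-efficacy with usability and with use exploratory.

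**The concern.** The word main covers five items in one place and one item in another, and no sentence says which governs. The Summary's version of the self-efficacy endpoint also describes only people who used the app. Read literally it is a change within the intervention arm. Yet section 3 says that the control group is there so that the effect of ordinary treatment is not mistaken for an effect of the intervention.

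What is at stake is the choice of headline result. Patients in rehabilitation may gain self-efficacy over 4 weeks with or without stickers. If the intervention arm improves and the difference from usual care is unremarkable, the Summary's wording would still let the within-arm gain be called the main result. The same applies to a good usability score or frequent scanning, for which no control value exists. Section 4.4 makes follow-on research depend on the pilot being successful and does not define success, so the label main carries more weight than it otherwise would.

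**Working it through.** The protocol gives no power calculation or error rate for this point, so there is no figure to reproduce. The check is a comparison of the sections.

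**Step 1. Level given to each Summary item.**

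| Item | Summary | Section 2 | Section 8.1 | Section 10 |
|---|---|---|---|---|
| Self-efficacy (ESES) | Main | Primary | Main (8.1.1) | Primary (10.1) |
| User experience | Main | Secondary (patients) | Secondary (8.1.2) | Secondary (10.2) |
| Usability (SUS) | Main | Secondary | Secondary (8.1.2) | Secondary (10.2) |
| Feasibility | Main | Not a separate objective | Secondary (8.1.2) | No separate analysis |
| Frequency of app use | Main | Other | Other (8.1.3) | Other (10.3) |

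Usability appears in 8.1.2 as "Usability (layout, interface, ease of use, relevance of content, etc", a sub-item of users' experiences. Main endpoints: 5 in the Summary, 1 in section 8.1.1. Of the 5 − 1 = 4 that differ, three are secondary and one is other in section 8.1. Where sections 2 and 10 place an item, they agree with 8.1.

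**Step 2. Which items have a control value.** The table in section 8.3 gives controls the ESES and demographics at the start and the ESES alone at the end. The SUS and interviews come from the intervention group and the physiotherapists, and frequency of use comes from the app log. So one item (ESES) is measured in both arms. Three (user experience, SUS, use) have no control value. Feasibility is a synthesis in which only the self-efficacy component has a comparator. Only the ESES can answer the primary objective.

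**Step 3. How the ESES endpoint is defined.**

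- Summary: "Self-efficacy quantified with Exercise Self-Efficacy Scale questionnaire before and after 4 weeks of using the application". This cannot describe the control arm.
- Section 3: controls complete the ESES before and after the intervention group's testing period.
- Section 8.3: both groups complete it at the start and after 4 weeks; this section also names the instrument and its range of 10 to 40.
- Section 8.1.1: silent on all three elements.
- Section 10.1: before-after tests in both arms, within and between groups, using paired or signed-rank tests. No single contrast is marked as the deciding one.

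Instrument and timing can be put together from sections 3 and 8.3. The contrast cannot: section 2 implies intervention versus usual care, but neither 8.1.1 nor 10.1 singles it out from the within-arm changes.

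**Step 4. What the contrast has to account for.** Section 4.2 concedes that allocation is not truly randomised, because patients without an NFC-compatible phone can enter only the control group. Baseline ESES may therefore differ between arms. A comparison of 4-week scores alone would carry that difference into the result, so the main contrast should use change from baseline or adjust for baseline.

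**The case against.** The strongest reply is that the Summary is only a condensed list. It has one heading for parameters, puts self-efficacy first, and states the comparison with usual care in its own Objective. The ranking is set out three times in the body, consistently. Sections 3 and 8.3 make clear that controls complete the ESES over the same period. The study is an exploratory pilot of about 30 patients with no power analysis, meant to inform later trials.

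Most of that stands, and it limits the point. The protocol as a whole does have a hierarchy, so a reader who infers from the Summary that there is none goes too far. What the reply leaves open is the contrast: the body ranks self-efficacy first without saying which self-efficacy comparison decides.

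Three other stronger readings are tempting and not supported:

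- *An inflated false-positive rate.* A reader might treat the five items as five tests at 0.05 and compute 1 − 0.95^5 = 0.226. The protocol plans no such family of tests. User experience and feasibility are not tested at all. The planned correlations concern association with the ESES, not the SUS score or the amount of use, and 10.1 calls them exploratory.
- *A pass mark for usability.* Section 8.3 describes a SUS of 68 as average and does not make it a success criterion. The Summary sets no such criterion for any item, so the trial cannot be said to be formally positive under it.
- *Self-efficacy as a second, competing endpoint in 8.1.2.* Section 8.3 says that feasibility will be judged from the data already gathered. The self-efficacy item there can be read as an input to that judgement and need not be removed.

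**Conclusion.** The point holds as an internal inconsistency with a reporting consequence. The Summary labels five items main where section 8.1.1 has one, and defines the ESES endpoint in a way that leaves out the control arm. Sections 8.1.1 and 10.1 do not fix the between-group contrast that the primary objective needs. Together these leave room to present a within-arm gain, or a usability or usage result without a comparator, as a main finding.

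The harm is selective emphasis and has no numerical size beyond the count of five against one. The conclusion assumes only that the Summary may be read or cited on its own. The weight is moderate: the study is exploratory, and the body of the protocol is consistent on ranking. The correction should be made because it is nearly free.

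**What to change.** 1. In the Summary, relabel the list to match 8.1. Main: self-efficacy. Secondary: usability, experiences of patients and physiotherapists, feasibility. Other: frequency of app use.
2. In the Summary, 8.1.1 and 10.1, define the main endpoint in the same words: the difference between intervention and usual care in change in ESES total score from baseline to 4 weeks. The 4-week score adjusted for baseline is an acceptable alternative; choose one.
3. In 10.1, mark within-arm changes as supportive and keep the SUS and use correlations as exploratory. Say that neither these nor results without a control value replace the main comparison.
4. The self-efficacy item under feasibility in 8.1.2 may stay, described as an input to the feasibility judgement.

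Cost: rewording of three places and a short note in 8.1.2, with no new data and no change to the target of 30 patients. Section 10.1 needs the most work, since its tests must be restated around the chosen between-group contrast. The sponsor gives up presenting the SUS or app use as a main result.

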1. INTRODUCTION AND RATIONALE

Improving patient health outcomes and decreasing costs are challenges currently faced by healthcare systems all over the world (Barello *et al.*, 2015; Elf *et al.*, 2015). Several trends are emerging to address these challenges, such as “patient-centred care” and “participatory healthcare”. Both trends represent acknowledged ways of engaging patients in the management of their health (Epstein *et al.*, 2010; Gruman *et al.*, 2010). Actively and efficiently engaged patients show improved clinical outcome and patient engagement represents a crucial factor for improving quality of care and increasing patient safety (Barello *et al.*, 2015; Schwappach, 2010). A concept called eHealth and its sub-concept mHealth (mobile Health) interventions are recognized to have a tremendous potential to promote patient engagement (Barello *et al.*, 2015; Hamine *et al.*, 2015). Further, eHealth interventions show promise for increasing medication adherence (Linn *et al.*, 2011). Possibly, physiotherapy adherence could be enhanced using eHealth interventions as well.

Although figures differ, it is assumed that at least half of rehabilitating patients does not adhere to their prescribed physiotherapy exercises, resulting in dissatisfactory treatment outcomes (S Frances Bassett, 2003; Sandra F. Bassett & Prapavessis, 2011; Engström & Öberg, 2005; Forkan *et al.*, 2006; Sluijs, 1991). During and after the transition from short-term (therapy under guidance) to long-term (autonomous) physical therapy, this share is likely to increase (Friedrich *et al.*, 1998). Furthermore, physiotherapists frequently interpret poor treatment outcomes as evidence of their treatments being inadequate, which in turn might lead to them making unnecessary treatment changes (S Frances Bassett, 2012). Either of these factors are likely contributing to why physiotherapy does not always result in the optimal outcome (Friedrich *et al.*, 1998).

As increasing exercise adherence leads to improved treatment outcome in various rehabilitation programs, this is an interesting field of research (Brewer *et al.*, 2000; Groth *et al.*, 1994; Lyngcoln *et al.*, 2005). However, within physiotherapy, adherence is a multi-dimensional concept not easily assessed and thought to be affected by many factors related to patient, healthcare provider and healthcare organization (S Frances Bassett, 2003; Kolt *et al.*, 2007; Miller *et al.*, 1997). Due to its broad concept, increasing adherence remains a challenge not likely solved with a single intervention (Martin *et al.*, 2005).

Sluijs *et al.* and Jack *et al.* noted three main patient-focussed factors regarding nonadherence: (1) Barriers perceived and encountered (“too little time”, “does not fit in daily routine”, “forgetfulness” and “pain”, among others), (2) lack of positive feedback and (3) degree of helplessness (Jack *et al.*, 2010; Sluijs, 1991; Sluijs *et al.*, 1993). An aspect involved in these three main factors is self-efficacy, which reflects an individual’s belief in his or her ability to engage in specific behaviours that will yield a desired outcome (Bandura, 1997). It is conceivable that the degree of self-efficacy is involved in nonadherence. Self-efficacy correlates with barriers such as pain and greater helplessness correlates with lower self-efficacy (Litt, 1988; Martin *et al.*, 2005; Shnek *et al.*, 1997). Positive feedback was shown to increase self-efficacy (Bandura, 1991; Champion & Lord, 1982; Ilgen *et al.*, 1979; Podsakoff & Farh, 1989). Indeed, previous research found that lower levels of self-efficacy were associated with lower adherence to a rehabilitation program (Chen *et al.*, 1999; Flynn *et al.*, 1995; Hall *et al.*, 2002; Woodgate *et al.*, 2005). Adhering to a home exercise program often requires lifestyle changes, such as changing habits and daily routine. Exercise adherence and self-efficacy were linked to lifestyle changes, thus empowering patients in changing their lifestyle might prove beneficial for these parameters (Bandura, 1998; Martin *et al.*, 2005; Sluijs *et al.*, 1998).

The Radboud REshape & Innovation Center has developed an eHealth intervention for this patient empowerment in collaboration with a company called Touchless Industries. Together, they have designed NFC-equipped (Near Field Communication) stickers accompanied by a smartphone app that provide visual reminders along with instruction videos at appropriate locations for exercises to be performed. With this intervention, we aim to increase physiotherapy self-efficacy in home exercise programs as compared to usual care.

These so-called “sticky reminders” seen above contain certain components and aspects that could help in increasing either adherence or self-efficacy, or to empower patients in changing their habits. The sticky reminders provide visual triggers in appropriate locations. In healthy people and likely in patients, such contextual cues were proven effective in changing habits (Stawarz *et al.*, 2015). The reminders engage the lack of positive feedback by enabling milestones and corresponding motivating

feedback in the application, which can be seen by the patients and are thought to improve adherence (Bassett & Petrie, 1999). Further, the application allows for daily feedback provided by patients (e.g. pain scores) that can be seen in a graphic representation by both patient and physiotherapist. This provides an indication of rehabilitation progress and complements the need for verbal feedback, which often proves erroneous (Sluijs *et al.*, 1998). Pain, correlated to self-efficacy, could be (partly) prevented via the provision of the daily feedback to the physiotherapist and subsequent adaptations in therapy (Parker *et al.*, 1993). Further, self-efficacy is positively affected by personalizing home exercise programs (Akinsola & Awofala, 2009). The sticky reminders will incorporate that by both allowing tailored exercise programs and providing a possibility to show videos of the patient, with spoken feedback from the physiotherapist. Such instructional videos might be effective in empowering patients in physiotherapy since instructional support was shown to enhance self-efficacy for learning (Sewell & St George, 2009).

In this mixed methods pilot study, we will present an eHealth intervention comprised of NFC-equipped stickers and an accompanying app. The intervention will be tested in a distinct target population consisting of patients suffering from Neuralgic Amyotrophy (NA) or lower extremity amputations. For these patients, physiotherapy is important in their rehabilitation for preventing or treating strain and coordination dysfunction (NA) or retaining gait and walking symmetrically with a prosthesis (amputation) (Christensen *et al.*, 1995; Frölke *et al.*, 2017; Leijendekkers *et al.*, 2017; [name] & van Engelen, 2007; Van Eijk *et al.*, 2016). With this (primarily) digital intervention, we aim to enhance self-efficacy of these patients during their physiotherapy home exercise programs as compared to usual care, where they receive written and verbal instructions and feedback. Next to self-efficacy assessment, we will gather user experiences and perception about usability, with which we will assess the feasibility of this intervention in physiotherapy.

2. OBJECTIVES

Primary Objective:

To study whether NFC-equipped sticky reminders increase physiotherapy self-efficacy in home exercise programmes as compared to usual care in rehabilitating patients suffering from Neuralgic Amyotrophy or a lower extremity amputation over a period of 4 weeks.

Secondary Objective(s):

To assess the usability of the app and user experiences with NFC-equipped sticky reminders for home exercise programmes in physiotherapy as perceived by rehabilitating patients suffering from Neuralgic Amyotrophy or a lower extremity amputation and how this could be improved.

Other Objective(s)

To determine whether the intervention is used, and thus whether observed effects in intervention group could be caused by the intervention.

3. STUDY DESIGN

This pilot is a controlled mixed methods feasibility trial.

The Radboudumc department REshape & Innovation Center in collaboration with two physiotherapy departments will execute the pilot. The envisioned duration of the project is five months. Patients will be included in April and May 2018, after which we will analyse data and publish results. The product-testing period is 4 weeks per patient. There will be an intervention group and a control group. The control group will only execute point 1 and 5 in the research design described below besides their regular treatment (excluding interview and SUS component). The control group is present to exclude conclusions based on treatment effects instead of intervention effects. The intervention group will go through all five steps. Millen et al. chose a similar study design, where they measured self-efficacy in cardiac rehabilitation (Millen *et al.*, 2009).

In the present course of therapy, supporting their home exercise program, patients suffering from Neuralgic Amyotrophy or a lower extremity amputation (using a socket or an osseointegrated prosthesis) receive a folder with written instructions on performing the exercises which can be consulted when needed. Patients give feedback during every hospital visit regarding their exercises and progression. In these sessions, the physiotherapist asks for information on the whole week schedule, whereas for patients it is hard to remember the exercises of the beginning of the week. To improve this, the osseointegrated prostheses patients keep a daily paper-based diary for pain scale, pain location, prosthesis wearing time and time spent on muscle exercises and standing or walking. Apart from this, patients do not register or monitor their progress in current course of therapy.

The introduction of the sticky reminders in combination with the app alters the method of registration compared to the present course, but the overall process remains the same. *Instead of written or spoken instructions and feedback, this information will be digitally provided and available.*

The patient process is described and depicted below.

1. **Baseline measurement:** To monitor self-efficacy patients are asked to fill out a validated self-efficacy questionnaire. This outcome is supposed to be the baseline value of the pilot. For extra information regarding the patient, demographic questions will be included in the questionnaire.
2. **Technology introduction:** In the first hospital visit, the patient will get all the necessary or desired information on the new technology. Following this meeting, patients have time to decide whether they want to participate in the pilot. After inclusion, patients receive help for installing the app and will get an introduction on how to use the application.
3. **Home registration:** After the regular physiotherapy appointment in the hospital, patients will receive exercises to execute in the home situation. These exercises are also linked to at least one NFC tag. These NFC tags are illustrated with a location, suitable for the exercises. Patients will discuss their personal appropriate locations for the NFC tags with their physiotherapist. When walking by the NFC tag, the patient can scan the tag with their personal smartphone, showing them a video of the corresponding exercise. All information that was previously provided in the folder is now handed to the patient via the video. The application registers the scanning of the tag on a secure server. If no prescribed exercises are performed within a predefined timeslot, the app will send a one-time push notification to the patient. At the end of the day, a tag will be scanned to show the daily report form. This daily report contains questions matching the regular treatment supplemented with questions on efficacy.
4. **Physiotherapy session:** Back in the hospital setting, the regular treatment is continued and the progress of the rehabilitation will be discussed. The app can support this session by presenting graphic representations of the daily feedback gathered with the daily reports. Step 3 and 4 will be repeated until the NFC tag trial period is over.
5. **Evaluation:** In the end, the questionnaire answered at the start is repeated as an end-measure, supplemented with a system usability scale (SUS) questionnaire. Elaborate opinions will be gathered by interviewing patients and physiotherapists in a semi-structured way. In semi-structured interviewing, a guide is used, with questions and topics that must be covered.

Sticking to your Exercises

[figure not shown]
However, in contrast to structured interviews, this conversational style of interviewing allows for gathering elaborate opinions.

The timeline is shown below. The control group and intervention group will undergo a different timeline:

- Control group:** The control group is present to exclude conclusions based on treatment effects instead of intervention effects. These participants will receive a questionnaire regarding exercise self-efficacy (specifically the Dutch translation of the Exercise Self-Efficacy Scale (ESES), validated in spinal cord injury (Nooijen *et al.*, 2013)), before and after the testing period of the intervention group. For extra information regarding the patient, demographic questions will be included in the questionnaires.
- Intervention group:** They will receive the ESES questionnaire before the testing period. After the testing period, this questionnaire will be handed out as well, supplemented with questions regarding usability (System Usability Scale or SUS (Brooke, 1996)). For extra information regarding the patient, demographic questions will be included in the questionnaires. Further, a semi-structured interview will be conducted with participants from the intervention group. We expect that patients need 15 additional minutes per day using the intervention as compared to usual care. Apart from the interview, no additional hospital visits are required.

A flow chart can be included to give an overview of the study design and the main procedures that subjects will undergo in the course of research

